An adaptive urn randomization procedure, ¹⁵⁵⁻¹⁵⁸ implemented using the Microsoft Access application gRand, will balance potential confounding variables among participants randomized to each condition and also will manage condition sizes. This method is recommended for trials of SUD treatments. ¹⁵⁵ Based on the population and outcomes of interest, factors on which the urn will operate are youth age, sex, baseline substance use severity, and a weighted percentage schedule for condition balance. The urn will minimize variability in these pre-treatment variables across the two conditions. To keep Assessors blind to condition, the Assessment Coordinator will conduct the randomization procedure immediately following a family's baseline assessment and will convey results directly to parents. The Coordinator also will inform the clinic intake worker of the randomization result so the family can be assigned to a CADC in the correct condition: CM+ or CM only.

DATA COLLECTION PROTOCOL

Assessors will meet with youth and parents for (1) a 2-hour, in-person baseline interview, (2) in-person, 1.5-hour follow-up assessments at 2-, 4-, 6-, 9-, and 12-months post baseline, and (3) 30-minute phone interviews at 1-, 3-, 5-, 7-, and 8-months. If youth and parent have to be assessed at different sessions, they will be scheduled within one week of each other. This schedule provides frequent measurement of constructs during active treatment (both CM+ and family-based CM are expected to last 5-6 months on average), while also providing a longer view on durability of change than is typical in adolescent SUD treatment research.¹⁹

To compensate for their time, families are paid \$50 for baseline and \$40 for each in-person follow-up assessment. Families will be paid \$10 for each brief telephone assessment (maximum total compensation = \$300). Based on our experience, 1.5- to 2-hour assessments rarely present a significant response burden, but Assessors are trained to use breaks with snacks and to attenuate circumstances that threaten validity of assessments. Participant protections are detailed in the Human Subjects Protocol and include IRB approval.

MEASURES

Multiple methods or perspectives will enhance construct validity. Consistent with intention-to-treat principles,

data from all time points will be collected even if families drop out of treatment.

Table 2. Research Instruments

Descriptive Variables [Baseline only]

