Structured Adolescent Interview¹⁵⁹ for demographics and to supply relevant data for the urn randomization.

Ultimate Outcomes [Months 0, 2, 4, 6, 9, & 12]

SUBSTANCE USE:

Urine samples collected by researchers from youth; lab testing for THC, synthetic THC, amphetamines, opiates, PCP, cocaine, and alcohol metabolites (EtG/EtS); selected lab's testing procedures are of high scientific quality.

GAIN¹⁵¹⁻¹⁵⁴ scales measuring self-reported youth substance use and substance-related problems; 16-item substance abuse index/substance dependence, substance problem scales assessing DSM-5 criteria for substance use disorders and lower severity symptoms, recovery environment risk and social risk subscales that predict substance-related problems in youth with substance abuse, and the substance frequency scale assessing substance use for past 90 days; GAIN scales have good reliabilities and sensitivity to change, and are highly associated with results from Form-90 and urine testing. ¹⁶⁰⁻¹⁶¹

EXTERNALIZING BEHAVIOR: Externalizing subscale of parent-completed **Child Behavioral Checklist** and corresponding subscale of **Youth Self Report**; ¹⁶² scales provide valid measures of youth externalizing behavior from multiple perspectives. ¹⁶³

Direct Target [Months 0, 1, 2, 3, 4, 5, 6, 7, 8, 9, & 12]

PARENT MANAGEMENT:

Alabama Parenting Questionnaire (APQ)¹⁶⁴ administered to youth and parents, measuring monitoring/supervision, positive parenting (social/tangible reinforcement), and consistent discipline (removal of privileges); scales have been used to document treatment outcomes and distinguish families of youth with and without behavior problems; ¹⁶⁴ scales have established reliability and validity; ¹⁶⁵ an additional rules and expectations subscale added to the APQ assesses enforcement of household rules.

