EXPERIMENTAL MEDIATION AND CAUSAL INFERENCE. The experimental mediation design emphasizes evidence supporting causal inferences, and there are important conceptual and statistical considerations. As reviewed by [name], ¹⁹⁹ by randomizing youth/parents, the effect of CM+ on parent management is a causal estimate. However, the effect of parent management on drug use and externalizing behavior is not straightforwardly causal, it is potentially influenced by unmeasured confounding variables. Following [name]'s

recommendations, and to support causal inferences, this is addressed in 3 ways. First, the enhancement design directly targets the mediator—increasing probability of a causal effect between mediator and outcome. Second, longitudinal measurements of the mediator and outcomes address temporal sequencing—demonstrating that mediator effects occur before outcome effects. Third, supplemental models evaluate confounding variables—providing evidence that mediator effects are not due to confounders.

MODEL FORMULATION. The underlying model is a mixed-effects latent growth curve model with repeated measurements (level-1) nested within youth/parents (level-2), implemented in Mplus (v7.31;¹⁹⁷). As reviewed by [name],²⁰⁰ there are several options for modeling longitudinal mediation. Flexibility of growth models for targeting phase-specific change²⁰¹ are leveraged and combined with parallel process models for mediation.²⁰² In a single model, there are separate change estimates for during- and post-treatment phases, directly addressing temporal sequencing of mediators and outcomes. The UDS outcome is modeled using a Bernoulli distribution, and remaining ultimate outcomes, direct targets, and indirect targets are modeled with normal distributions. Time terms are computed using assessment dates.²⁰³ Treatment condition is a youth/parent-level predictor (level-2; CM = 0, CM+ = 1), and cross-level interactions are specified between condition and level-1 growth and phase terms. Models, as indicated, control for age, sex, race, ethnicity, SES, and treatment history. Likewise, preliminary models test, and control, for differences in outcomes across therapists and clinics. Follow-up models determine whether individual paths and mediated effects differ for males and females.

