STATISTICAL TEST FOR MEDIATION. The test for mediation is based on the product of coefficients (i.e., $\alpha\beta$) with asymmetric bootstrapped *SE*s and 95% CIs for the product.²⁰⁴ This test requires estimation of two parameters and their *SE*s, where, for example, α is the effect of CM+ on parent management and β is the effect of parent management on substance use and externalizing behavior. Parameters are obtained from Mplus and supplied to PRODCLIN²⁰⁵ for the asymmetric boostrapped *SE*s and CIs. This approach offers enhanced statistical power²⁰⁶ and applies both to multilevel data²⁰⁷ and longitudinal mediation.²⁰⁰

EVALUATION OF SPECIFIC AIMS

AIM 1: DETERMINE WHETHER PARENT MANAGEMENT SKILLS (DIRECT TARGET) MEDIATE THE EFFECT OF TREATMENT ON YOUTH SUBSTANCE USE & BEHAVIOR PROBLEMS (ULTIMATE OUTCOMES). The test for mediation requires the coefficient and SE for CM+'s effect on parenting (a-path) and parent management's effect (controlling for treatment) on substance use and externalizing behavior (b-path). Of note, a preliminary model evaluates the direct effect of CM+ on substance use and externalizing behavior (c-path), though as noted by [name], ¹⁹⁹ mediation should be tested regardless of this path's significance.

a-path. This model is specified with 11 repeated measurements of parenting as the outcome. To address temporal sequencing, the model estimates separate change rates for during- and post-treatment phases. This is tailored to each youth's course of treatment using coding strategies for discontinuous (piecewise) change (see Singer and Willett²⁰¹). Changes during treatment phase are modeled with linear and quadratic terms for number of months since baseline. A dichotomous phase indicator differentiates post- and during-treatment measurements, and post-treatment change is modeled as linear and quadratic terms for number of months since treatment end. This provides three estimates: during-treatment slope (estimate of interest for mediation test), overall shift in parenting levels from during- to post-treatment, and post-treatment slope.

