b-path. This model is more complex, simultaneously evaluating the mediator and outcome processes. To obtain this coefficient, the a-path is modeled along with the outcome model (c-path; testing for differences between CM+ and CM on substance use and externalizing behavior). With fewer outcome measurements, the model includes a during-treatment slope term and indicators to differentiate 9- and 12-month assessments, providing three estimates: during-treatment slope, change at 9 months, and change at 12 months. To obtain the b-path coefficient, a regression is specified with *during-treatment mediator slope* as a predictor of *outcome at 9 and 12 months*. This provides a targeted test of mediation, with during-treatment change in the mediator as a predictor of post-treatment outcomes.

Ethnicity effects. In close consultation with project consultant [name], and to address potential for differential effects across project clinics, formal moderated mediation tests can be performed.²⁰⁸⁻²⁰⁹ These tests determine whether observed mediation effects differ for Latino and non-Latino youth/parents. Sample size means that results are hypothesis-generating and thus will focus on estimation of confidence intervals. The same approach will be used to evaluate moderated mediation for ethnicity in Aims 2 and 3.

Confounding variables. Although randomization, the enhancement mediation design, and models addressing temporal sequencing increase the likelihood of valid causal inferences for mediation, a remaining assumption is that there are no unmeasured confounding variables for the mediator's effect. Cox et al.²¹⁰ recommends sensitivity analyses for confounder bias be used. First, VanderWeele's²¹¹ formulas identify youth/parents with the same value on the mediator but different values on the outcome, as well as youth/parents with the same value on the mediator across both CM and CM+ groups. Second, residuals from the models just detailed should be uncorrelated, and Mplus code from Imai et al.²¹² is used to determine whether the mediated effect differs based on unmeasured pre-treatment variables. Third, Mauro's²¹³ correlational method evaluates the sources of error variance from the mediation model, determining how large the effect of an omitted variable

would need to be to negate the mediated effect.

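### The growth models appear to leave the CM+ vs CM difference at month 0 free although baseline precedes randomization; fixing it at zero would be a low-cost gain in precision, of uncertain size

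*Combined protocol and SAP*

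**What the plan says.** **Model Formulation:** "Treatment condition is a youth/parent-level predictor (level-2; CM = 0, CM+ = 1), and cross-level interactions are specified between condition and level-1 growth" and phase terms. The covariates listed there are demographic and socioeconomic variables plus treatment history. None is the baseline value of the mediator or of an outcome.

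**Aim 1, a-path:** "This model is specified with 11 repeated measurements of parenting as the outcome", and "Changes during treatment phase are modeled with linear and quadratic terms for number of months since baseline". Table 2 schedules parent management at month 0 as well as at the follow-ups, so baseline is part of the outcome vector.

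**Aim 1, b-path (which contains the c-path model):** the outcome model is described as "providing three estimates: during-treatment slope, change at 9 months, and change at 12 months". Table 2 lists "Ultimate Outcomes [Months 0, 2, 4, 6, 9, & 12", so baseline is an outcome measurement here too.

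**Randomization to Conditions:** "the Assessment Coordinator will conduct the randomization procedure immediately following a" family's baseline assessment. The urn balances age, sex and baseline substance use severity. It does not balance parenting or externalizing behavior.

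No section fixes the month-0 arm difference at zero. No section says outright that such a difference is to be estimated or reported.

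**The concern.** With time zero at baseline, a condition main effect in a growth model is the arm difference at month 0. No family has been assigned at that point, so the true difference is zero by design. If the term is estimated anyway, the slope contrast cannot borrow from the baseline comparison, and error in the baseline measurements stays in the estimated difference in change. Fixing the term at zero (a constrained longitudinal analysis) makes the baseline score work much as a covariate would.

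The a-path slope contrast is the randomized leg of the mediated effects in Aims 1 and 2, and the standard error of the product depends on its standard error. What is at stake is therefore precision in alpha and, for the continuous outcomes, in the c-path.

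**Working it through.** **1. The plan's own figure.** Statistical Power for Mediated Effects gives a-path power above .90 at R² = .07 and N = 155 (172 × 0.90 = 154.8). As a single-predictor regression, noncentrality = 155 × .07/.93 = 11.67, and two-sided .05 power is .924. The stated figure reproduces.

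**2. Set-up.** From the plan: monthly parenting visits 0 to 6 and N = 155. Assumed: 1:1 allocation, complete visits, treatment ending at month 6, and the variance components. Scale the baseline variance to 1. Let s be the residual share, d the SD of true 6-month change and r the intercept-slope correlation. The contrast is 6 × (condition × month) with linear growth. Visits 0 to 6 have mean 3 and sum of squares 28. For one family's fitted line:

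- Var(change) = d² + 36s/28
- Var(intercept) = (1 − s) + s(1/7 + 9/28)
- Cov = r·d·√(1 − s) − 18s/28

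With the month-0 difference free, the contrast variance is (4/155) × Var(change). With it fixed at zero, that is multiplied by 1 − Cov²/[Var(intercept) × Var(change)].

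**3. Central case: s = .4, d = .7, r = −.2.** Var(change) = .490 + .514 = 1.004. Var(intercept) = .600 + .186 = .786. Cov = −.108 − .257 = −.366.

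- Free SE = √(4 × 1.004/155) = .161
- Ratio = 1 − .1336/.7891 = .83
- Constrained SE = .161 × √.83 = .147

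The variance falls by 17%. Adding the planned quadratic during-treatment term gives a ratio of .85, a 15% fall.

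**4. Dependence on r (s = .4, d = .7, linear).**

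| r | variance ratio | reduction |
|---|---|---|
| −.4 | .72 | 28% |
| −.2 | .83 | 17% |
| 0 | .92 | 8% |
| +.2 | .97 | 3% |
| +.4 | 1.00 | 0% |

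**5. Ranges for s = .3 to .5 and d = .5 to 1.0.**

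- a-path, r from −.4 to 0: ratio .67 to .97. The low end is s = .5, d = .5, r = −.4.
- a-path, r from +.2 to +.4: ratio .90 to 1.00.
- Continuous outcomes, visits 0, 2, 4, 6: ratio .64 to .95 for r from −.4 to 0, with the gain again able to vanish at positive r.

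**6. The planned piecewise model.** This used all visits to month 12 with the phase terms, intraclass correlation .3 to .7, SD of true change 0 to 1.0 times the intercept SD, and r from −.3 to +.3 (21 scenarios).

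| Contrast | ratio | median |
|---|---|---|
| a-path, linear-only slope | .60 to 1.00 | .82 |
| a-path, initial slope with quadratic | .58 to .93 | .74 |
| a-path, 6-month change with quadratic | .70 to 1.00 | .84 |
| c-path, during-treatment slope | .57 to 1.00 | .77 |
| c-path, change at 9 or 12 months | .71 to 1.00 | .84 |

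The larger gains come from low intraclass correlations. The constraint never raised the variance.

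**7. Therapists.** Three therapists deliver each arm. If a share p of true-change variance lies between therapists, both variances in step 3 gain 2pd²/3. For p = .05 this is .0163, and the ratio becomes (.0215 + .0163)/(.0259 + .0163) = .90. For p = .01, .05 and .10 the 17% gain becomes 15%, 10% and 7%.

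**8. Effect on the mediation test.** The plan states power of .85 for the beta-path and .83 for the mediated effect, using a Sobel standard error. The Sobel statistic is 1/√(1/z_α² + 1/z_β²). It cannot exceed the smaller of |z_α| and |z_β|, so mediated-effect power cannot exceed beta-path power. Taking the plan's figures at face value, even a perfectly precise alpha adds at most .85 − .83 = .02.

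**The case against.** A free intercept contrast is a standard and valid parameterization. Under randomization the slope contrast is unbiased and its test is sound. A reader might infer that chance imbalance in baseline parenting biases alpha through regression to the mean. It does not: the imbalance averages zero over randomizations and is already reflected in the standard error, so this is the same precision loss under another name. This part of the objection stands in full.

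The free term is also inferred. The a-path and b-path sections list slopes, shifts and changes, not a baseline arm difference. A reader might say that the plan commits to estimating one; it is silent. That silence is a reason to state the parameterization.

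The size is uncertain. A reader might turn the central case into a headline of about 187 families instead of 155 (155/.83). That rests on an assumed correlation of −.2 and ignores therapist variation; with r = 0 the gain is 8%, and at positive r it can disappear.

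Finally, the change is not free of assumptions. In a growth model the constraint acts on the model-implied month-0 mean, so a poorly fitting curve could move error into the slope contrast. The urn already limits imbalance in substance use severity, so for those outcomes the gain lies more in the reported standard error than in the true variability of the estimate. The Bernoulli urine-screen model was not computed.

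What survives is narrower: the expected month-0 difference is zero, the plan does not use that fact, and across the assumed scenarios using it never raised the variance of a contrast.

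**Conclusion.** The point holds as an efficiency improvement, not as an error of validity. For the a-path 6-month change, the variance reduction is 0% to about 33% over residual shares of 30% to 50%, true-change SDs of 0.5 to 1.0 and intercept-slope correlations of −.4 to +.4. Lower intraclass correlations, or the initial slope as the contrast, can give more; between-therapist variation in change gives less. None of these quantities is in the documents, so no single figure should be quoted as the loss.

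The gain for the alpha × beta test is modest on the plan's own figures: about two points of power at most under the Sobel method used for its simulation. The documents support neither a claim of bias nor one of inadequate a-path power, which is already stated as above .90. For the c-path the conclusion covers continuous outcomes only.

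**What to change.** In Model Formulation, state that the condition effect at month 0 is fixed at zero in the a-path model and in the c-path models for the continuous outcomes, and that the condition-by-growth and condition-by-phase terms are kept. Name the unconstrained model as a sensitivity analysis. If the two slope contrasts differ materially, examine the fit of the growth curve near baseline before interpreting either.

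The cost is a sentence or two of wording, one fewer parameter in each model and one additional run. No new data, visits or families are needed. Settling it before outcomes are compared by arm also removes a later choice between the two parameterizations.

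### Baseline substance use severity balances the randomization but is in no stated model, so a measured, plausible confounder of the b-path goes unadjusted

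*Combined protocol and SAP*

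**What the plan says.** Randomization to Conditions lists what the urn uses: "factors on which the urn will operate are youth age, sex, baseline substance use severity, and a weighted percentage schedule for condition balance". Table 2 has a baseline-only interview, used "for demographics and to supply relevant data for the urn randomization". Randomization follows the baseline assessment, so a severity value exists before assignment.

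Model Formulation gives the covariates: "Models, as indicated, control for age, sex, race, ethnicity, SES, and treatment history". Age and sex carry over from the urn; severity does not. The Aim 1 to 3 paragraphs do not add it. Aim 1 describes the b-path as adjusted for treatment, and Aim 3 describes its b-path as adjusted for parent management.

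Experimental Mediation and Causal Inference accepts that "the effect of parent management on drug use and externalizing behavior is not straightforwardly causal, it is potentially influenced by unmeasured confounding variables". It promises supplemental models for confounders but names no variables. The Confounding variables paragraph under Aim 1 starts from the position that "a remaining assumption is that there are no unmeasured confounding variables" and sets out sensitivity methods for that assumption, including one that asks how strong an omitted variable would have to be.

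**The concern.** The urn exists to balance potential confounders between arms, and the plan chose severity as one of them. Balance between arms protects the randomized comparisons. It does nothing for an association between a post-randomization slope and a later outcome within the sample. That association is the b-path: how fast parenting changed during treatment is related to outcomes at 9 and 12 months.

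Families of more severely affected youth may change their parenting faster or slower, and severity may also predict later use and behavior. If both hold, part of the b coefficient is severity, and the product of coefficients inherits the shift. The direction is not known in advance. A sensitivity analysis for unmeasured variables does not replace adjustment for a variable already on file.

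A smaller issue concerns the randomized contrasts. Leaving a balanced prognostic factor out of the model makes the standard error of the condition effect somewhat too large.

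**Working it through.** **The plan's own figures.** Statistical Power for Mediated Effects uses N = 155 (172 × 0.9 = 154.8), R² = .07 per path, a-path power above .90 and b-path power of .85. A noncentral F test at N = 155 and R² = .07 gives .92 for the a-path, which agrees. A simple single-level regression gives .91 for the b-path. The plan's growth-model parameters are not stated, so .85 cannot be called wrong, and it is used below as given.

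**b-path inputs.** Planned standardized beta = √.07 = .2646. Power of .85 at two-sided .05 implies SE = .2646 / (1.960 + 1.036) = .0883.

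**b-path formulas.** Let r_m be the correlation of severity with the mediator slope, and r_y its correlation with the later outcome beyond what the model already holds. Both are assumed.
- Shift in b ≈ r_m × r_y, and m = shift / SE.
- Null rejection = Φ(−1.96 + m) + Φ(−1.96 − m).
- Power if the shift opposes the true effect = 1 − Φ(1.96 − (.2646 − shift)/.0883).

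| r_m × r_y | Shift | % of .2646 | m | Null b rejected | Power, opposite sign |
|---|---|---|---|---|---|
| .1 × .2 | .02 | 8% | 0.23 | .056 | .79 |
| .2 × .2 | .04 | 15% | 0.45 | .074 | .72 |
| .2 × .3 | .06 | 23% | 0.68 | .104 | .64 |
| .3 × .3 | .09 | 34% | 1.02 | .175 | .51 |

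A single-level simulation checks the third row (N = 155, true b = 0, r_m = −.2, r_y = .3, 4,000 replications). Without severity, bias is −.065 and rejection .118. With severity, bias is .000 and rejection .055.

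**Randomized a- and c-paths (Aims 1 and 2).** Let r be the assumed correlation of severity with the modelled change, with exact balance on continuous severity. These are upper bounds. Formulas: SE ratio = 1/√(1−r²); true size of a .05 test = 2(1 − Φ(1.96/√(1−r²))). For power, d = 2√(.07/.93) = .549, ncp = d√(155/4) = 3.416 and s = √(1−r²). Power is 1 − Φ((1.96 − ncp)/s) with severity omitted and 1 − Φ(1.96 − ncp/s) with it adjusted.

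| r | SE too large by | True size | Power, omitted | Power, adjusted |
|---|---|---|---|---|
| .2 | 2% | .0455 | .931 | .937 |
| .3 | 5% | .0399 | .936 | .947 |
| .5 | 15% | .0236 | .954 | .976 |

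With no effective balance, the test has its nominal size, power with severity omitted is .927, and adjustment only narrows the interval.

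**Placement.** The condition effect enters through growth terms: "cross-level interactions are specified between condition and level-1 growth and phase terms". In a simulation with 7 monthly waves, N = 156 and an assumed slope reliability of .6, the SE of the slope contrast was .160 without severity on the slope; adding severity to the intercept alone left the slope contrast unchanged. With severity on the slope it was .157, .153 and .139 for r = .2, .3 and .5. Severity therefore has to predict the slope to do any work there.

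**The case against.** The strongest reply is that the b-path harm is hypothetical. No section calls severity a confounder or gives a correlation. All youth have a current substance use disorder and are suited to outpatient care, which may narrow the range of severity and weaken both correlations. The size follows the inputs: assumed correlations of −.3 and .5 in the single-level simulation give null rejection of about .50, while .1 and .2 give .056. The SE of .0883 is also back-solved from a power figure that a simple model does not reproduce. All of this stands, so the b-path figures are illustrations only.

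A second reply is that month-0 outcome values are already in the growth models. For substance use outcomes on the same scale as the severity measure, they carry part of it. Other outcomes have their own month-0 values, which may overlap with severity to an unknown degree. But no regression of the mediator slope or of the later outcomes on baseline severity is specified, and a change score need not help. In a simulation with r_m = −.1 and r_y = .5, using change from baseline turned a bias of −.056 into +.052. Treatment history, which is listed, is at best a proxy.

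Third, the promised supplemental models might include severity. They neither assign nor exclude it.

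A reader might go further in two directions that the documents do not support. One is that making covariates conditional contradicts the statement in Scientific Rigor about age and sex. Both are urn factors and listed covariates, and follow-up models examine sex, so that statement is met. The other is that clinic is neglected. The plan says otherwise: "Likewise, preliminary models test, and control, for differences in outcomes across therapists and clinics".

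**Conclusion.** The omission is real on the text: severity is a balancing factor, measured before assignment, and absent from every stated model. Its consequence is minor.

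A reader might infer that the treatment comparison is biased. It is not. On the randomized a- and c-path contrasts the cost is slight conservatism or lost precision, with power above .90 either way. A reader might also infer that the b-path is shown to be confounded. It is not: confounding is plausible because severity is the baseline level of an ultimate outcome, but nothing in the documents establishes its size or sign. Under the assumed residual correlations, b shifts by .02 to .09 (8% to 34% of the planned value) and a null b-path is rejected .056 to .175 of the time, with .06 and about .10 at the middle illustration. The same reasoning applies to Aim 2's b-path and to Aim 3, where the predictors in both paths are non-randomized slopes.

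Nor would adjustment be sure to remove all confounding by severity. The measure and its coding are not defined, and a coarse urn category would leave some behind.

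**What to change.** Add baseline substance use severity to the covariates in Model Formulation and name the measure: the continuous baseline score where available, otherwise the urn variable. State that severity, age and sex are always included, not only where indicated. Enter all three as predictors of:
- the mediator intercept and during-treatment slope, in all aims;
- the 9- and 12-month outcomes in the b-path regression, in all aims;
- the terms that carry the condition effect in the a- and c-path models.

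Other growth and phase terms need not carry them. For substance use outcomes on the same scale as the severity measure, the month-0 value already does part of this work.

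The cost is one or two sentences and no new data. The downside is extra parameters at N of about 155. On every term, each covariate adds up to 6 coefficients in the a-path model and 4 in the outcome model, so three covariates add up to 3 × (6 + 4) = 30, with some convergence risk in a joint model. The restricted placement limits this. Counting the mediator intercept, the linear slope and the two later outcomes gives 3 × 4 = 12. Adding the quadratic slope term and the outcome's during-treatment slope gives 3 × 6 = 18.
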